## ii. List of Abbreviations

Define all unusual or 'technical' terms related to the trial. Add or delete as appropriate to your trial. Maintain alphabetical order for ease of reference.

AE	Adverse Event
API	Application Programming Interface
ASM	Active Symptom Monitoring
ASSIST	Alcohol, Smoking and Substance Involvement Screening Test
AWS	Amazon Web Services
CDS	Calgary Depression Scale
CGI	Clinical Global Impression
CI	Chief Investigator
CRF	Case Report Form
DPIA	Data Protection Impact Assessment
DRM	Digital Remote Monitoring
DWQ	Dunn Worry Questionnaire
EHR	Electronic Health Record
ERG	Expert Reference Group
EWS	Early Warning Signs
FoRSe	Fear of Recurrence Scale
GAD	Generalised Anxiety Disorder
GCP	Good Clinical Practice
GDPR	General Data Protection Regulation
GPS	Global Positioning System
HEI	Higher Education Institution
ICH	International Conference for Harmonisation
ICMJE	International Committee of Medical Journal Editors
IG	Information Governance
IN	Involvement Network
IRAS	Integrated Research Application System
LEAP	Lived Experience Advisory Panel
MARS	Medication Adherence Rating Scale
NHS	National Health Service
NHS R&D	National Health Service Research & Development
NICE	National Institute for Health and Care Excellence

PANSS	Positive and Negative Syndrome Scale
PCPW	Perceived Criticism & Perceived Warmth Scale
PI	Principal Investigator
PIS	Participant Information Sheet
PMG	Project Management Group
PPI	Patient and Public Involvement
PSM	Passive Symptom Monitoring
PSSUQ	Post-Study System Usability Questionnaire
PSYRATS	Psychotic Symptom Rating Scales
RDMS	Research Data Management System
REC	Research Ethics Committee
REDCap	Research Electronic Data Capture
RSG	Research Steering Group
SAE	Serious Adverse Event
SAP	Statistical Analysis Plan
SMS	Short Message Service
SOP	Standard Operating Procedure
UoM	University of Manchester
WSAS	Work and Social Adjustment Scale

### iii. Study Summary

Conventional methods of monitoring and assessing psychosis involve face-to-face assessments that rely on individuals recalling their symptoms and emotional states over the period since their last assessment. Understandably, recall can be inaccurate, resulting in imprecise assessment and treatment planning, and assessment is not frequent enough to detect early warning signs, thereby increasing the risk of relapse.

The study aims to recruit a cohort of relapse-prone individuals sufficient in size, collect passively and actively sensed data, with high sampling frequency, to develop a risk prediction model for estimating an individual's risk of relapse, which gets updated as more information becomes available about them over time. Moreover, the study aims to develop an adaptive sampling regime for maximising engagement and information obtained from digital remote monitoring (DRM); that is, asking the right questions, at the right frequency and time, for the right individuals. This will enable relapse to be predicted more accurately.

Study Title	Can we use information from electronic devices (e.g. phones) to predict if someone will have a relapse of psychosis?	
Short Title	CONNECT	
Objectives	
 
1. To develop a scalable digital platform that combines active and passive remote symptom monitoring, along with clinical assessments and a relapse prediction algorithm.
 
2. To predict psychosis relapse
 
3. To examine the utility of passive data
 
4. To develop an adaptive sampling framework
 
	
Study Design	Prospective, observational (non-randomised) non-interventional study with an in-built process evaluation and assessment of feasibility and acceptability of wearable devices, using commercially available wearable technology and smartphone sensors, representing no change to the usual care or treatments of participants due to participation.	
Study Participants (planned sample size)	Relapse-prone individuals with experience of psychosis ( $n = 1100$ )	
Study Duration	47 months	
Planned Study Period	August 2023 - December 2026	
	Outcomes	Outcome Measures
Primary	To derive and validate a personalised risk prediction algorithm to estimate the short-term risk of psychosis relapse	Clinical relapse, occurring within the next 7 or 28 days, measured every 4 months
Secondary	To derive and validate an adaptive sampling regimen for maximising engagement and information obtained from digital remote monitoring (DRM)	Disengagement with DRM devices

	Acceptability of a wearable device	Assessment of data collected; satisfaction questionnaire
	Acceptability of DRM and study procedures	Participants report procedures are acceptable via qualitative interviews and satisfaction questionnaire
Eligibility Criteria	
Inclusion criteria:
 
 
(i) Adults (16 years and over);
 
(ii) within the past two years have had at least one acute episode of psychosis (including relapse and first episode) leading to an unscheduled episode of acute care, including inpatient admission or acute home treatment/crisis intervention;
 
(iii) received a clinical diagnosis of, or confirmed by the treating clinician to meet the criteria of, schizophrenia spectrum disorder (ICD10 F20-29);
 
(iv) current presentation does not include severe acute symptoms;
 
(v) in accordance with the Mental Capacity Act, mental capacity will be assumed. If there is any doubt, then a capacity assessment will be carried out by a clinician from the study team or the responsible clinician.
 
 
Exclusion criteria: Experienced a recent relapse within the previous 12 weeks as confirmed by the treating clinician; non-English speaking.
	
Statistical Methodology and Analysis	
Extraction of sensor features; estimate association between these features and clinical status using mixed-effects models and unsupervised machine learning.
 
Regression modelling and other supervised machine learning approaches to develop risk prediction algorithm.
 
Information and decision theoretic methods to build adaptive sampling algorithm.
 
Qualitative methods (e.g. Framework analysis) to measure acceptability.
	

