### 3 Objectives and Outcome Measures/Endpoints

#### 3.1 Aims

The aims of this study are to collect sufficient data that will enable us to derive and validate:

- i) a risk prediction model that can use actively and passively collected data from DRM to accurately (and dynamically through time) predict an individual's risk of clinical relapse occurring within the next 7 or 28 days;
- ii) an adaptive sampling regimen for maximising engagement and information obtained from DRM.

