## **4 Study Design**

### **4.1 Design**

Prospective, observational (non-randomised, non-interventional) study with an in-built process evaluation and assessment of feasibility and acceptability of wearable devices, using commercially available wearable technology and smartphone sensors, representing no change to the usual care or treatments of participants due to participation. There is no control comparison group, or randomised group allocation.

We aim to recruit 1100 relapse-prone individuals with a schizophrenia spectrum diagnosis. To achieve our objectives, we will recruit one cohort (data will be split into two groups):

- i) Group 1 ( $n = 800$ ): in which we will derive and internally test a personalised relapse risk prediction algorithm using ASM items, passively collected behavioural, environmental and contextual data, integrated using machine learning (see statistical analysis section for details of the methods). We will also develop the adaptive sampling algorithm.
- ii) Group 2 ( $n = 300$ ): in which we will apply and temporally test the risk prediction algorithm and the adaptive sampling algorithm from Group 1. Note the adaptive sampling algorithm will not change the data collection in any way, nor will it be used to monitor, prevent or treat psychosis; we will simply use the data collected to test the algorithm.

This design of derivation/internal validation and subsequent temporal validation is appropriate to assess the algorithm's validity. Group 2 acts as a temporal validation set to test the prediction model and the adaptive sampling model on previously unseen individuals (recruited latest in time).

A future study will examine whether our predictive and adaptive sampling algorithms can improve clinical decision-making on early intervention for psychosis relapse (but this will not be tested in the proposed study).

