#### **6.4.3 Adaptive sampling algorithm development (Research questions 6 and 7)**

We will use the data collected in Group 1 to develop an adaptive sampling algorithm to allow the time and frequency of input requests from users to be optimised. Existing approaches for adaptive sampling are primarily in the health screening literature, where the problem is to optimise the timing of the next screening test (e.g. cancer screening). We will use such approaches to underpin our methods development by extending them to suit ASM for psychosis. We will begin by summarising overall patterns of engagement in Group 1 and use this to learn ‘what drives engagement’. Specifically, we will use both simple descriptive statistics of associations between participant characteristics and engagement with the app and apply latent class analyses to identify subgroups with different engagement patterns (building on our existing work ([name], et al., 2018) (Hulme, et al., 2021)) for hypothesis generation purposes. We will also model which factors (including demographics, histories of symptom response and patterns of response) predict engagement; outcomes for such models will include time-to-drop-out and intermittent non-response. This would imply a prediction model where stable, low symptom severity leads to sustained disengagement (Research question 7). Based on the learning from the generative models, we will build adaptive sampling models by considering a decision theoretic framework. This works by trading off, at any given time, what the value of requesting an observation would be (in terms of better predicting relapse, and ultimately improving clinical decisions), versus the cost of requesting the observation (e.g. possible disengagement of the user through alert fatigue). We will consider a number of approaches (Research question 6) including Hidden Markov models (in which observation frequency depends upon latent state, as we have explored previously (Hulme, et al., 2021) ([name], et al., 2018)), and joint models for longitudinal and time to event data (Rizopoulos, et al., 2016). We will simulate the action of the adaptive sampling model by subsampling from the Group 1 dataset. We will then explore how the risk prediction algorithm (discussed above) performs based on the now reduced data; i.e., to explore if the model on the subsampled data of Group 1 achieves comparable performance to the prediction model on the full Group 1 data. Based on our learning here, we will select the adaptive sampling algorithm that best trades off the most accurate and timely relapse predictions, with minimal input demands on the user.

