
#### **6.4.4 Algorithm validation (Research questions 4, 1 (cont), 6 (cont))**

We will use Group 2 ( $n = 300$ ) to temporally validate both the risk prediction model and the adaptive sampling algorithm developed in Group 1, providing unbiased estimates of predictive performance of each. Here, we will apply the risk prediction model (as developed and selected from Group 1; see above) to each participant in Group 2. We will examine the performance of this final model (in Group 2) in terms of calibration and discrimination using all of the aforementioned metrics. We will additionally aim to determine the clinical utility of the model (within Group 2) using decision-curve analysis, comparing ‘net benefit’ against extremes of a ‘treat-all’ vs. ‘treat-none’ approach across all combinations of risk threshold. The most basic interpretation of a decision curve is that the model with the highest net benefit at a particular threshold has the highest clinical value.

We will compare the performance of the developed algorithm (from Group 1) against existing (previously published) ‘static’ prediction algorithms (that are based only on baseline information and do not make use of the longitudinal or high fidelity data) in Group 2, on all of the metrics above (Research question 4).

For the adaptive sampling algorithm validation, we will subsample the data collected in Group 2 according to the adaptive sampling algorithm and evaluate the reduction in burden on participants and ensure that model performance of the risk prediction model is minimally affected by the reduction in available data. We will then use the validated adaptive sampling algorithm to further tailor the risk prediction model.

Note the adaptive sampling algorithm will not change the data collection in any way, nor will it be used to monitor, prevent, or treat psychosis; we will simply use the data collected to test the algorithm. There will be no change to the usual care or treatments of participants in this study due to testing of the adaptive sampling algorithm.

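### Disengagement cannot validate the adaptive sampling regimen, because nobody is prompted under it; the design supports a claim about requests saved and prediction retained, and the disengagement cost it trades off has to be assumed

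*Protocol*

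**What the plan says.** The secondary aim appears in two places. The Study Summary gives it as "To derive and validate an adaptive sampling regimen for maximising engagement and information obtained from digital remote monitoring (DRM") and pairs it with the measure "Disengagement with DRM devices". Section 3.1 puts the words derive and validate in front of "an adaptive sampling regimen for maximising engagement and information obtained from DRM".

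The design is then fixed so that the regimen is never used. Section 4.1 says "Note the adaptive sampling algorithm will not change the data collection in any way" and "There is no control comparison group, or randomised group allocation". Section 6.4.4 repeats the statement about data collection and adds "we will simply use the data collected to test the algorithm".

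Section 6.4.3 models time to drop-out and intermittent non-response under the study's own prompting. It then builds a decision rule that weighs the value of an observation against "the cost of requesting the observation (e.g. possible disengagement of the user through alert fatigue"). The rule is tried out by subsampling Group 1. In Group 2, section 6.4.4 again subsamples, judges the result by reduced burden and preserved performance of the relapse model, and afterwards calls the algorithm validated.

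**The concern.** An outcome measure can validate a regimen only if it could differ with and without that regimen. Here it cannot, because all responses, gaps and drop-outs arise under the study's own prompts. Deleting some of the answers afterwards does not change who stayed.

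The second difficulty lies in the cost term. Disengagement caused by a request is a causal effect of prompting. To learn it, the data must show how people behave under different prompt frequencies for reasons unrelated to their state. The protocol describes no such variation.

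Two things are at stake. A reader of the summary and 3.1 could take the final regimen as shown to keep people engaged, when the study will have shown that fewer requests cost little in prediction. The regimen chosen also rests partly on a quantity that the analyst has to assume.

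**Working it through.** The protocol gives no rate, effect size or power for this outcome, so there is no figure to reproduce. The check sets the sections side by side, then gives a simple identification argument.

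**Step 1. What each section can show.**

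| Place | Content |
|---|---|
| Summary, 3.1 | Validate a regimen whose stated goal is engagement; the summary's measure is disengagement |
| 4.1, 6.4.4 | Data collection unchanged; 4.1 adds that there is no control or randomised group |
| 6.4.3 | Disengagement is modelled under the study's own prompts |
| 6.4.4 | Validation criteria are burden reduction and retained prediction |

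Participants exposed to the regimen: 0 of 1100. For any two candidate regimens, the difference in observed Group 2 disengagement is exactly zero by construction.

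**Step 2. Variation in prompting.** Section 5.8.1 describes one evening notification window with at most one completion a day. No study-set difference in frequency between participants is described. Some variation in burden does exist:
- pauses chosen by the participant (5.9);
- supplementary items triggered by high scores, and item sets altered as symptoms change (5.8.1);
- use of some components of the system but not others (5.8.1).

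The pauses are close to disengagement itself, and the item changes follow symptoms. By the protocol's own account, disengagement may come with a stable condition (1.4, 6.4.3) and with declining mood (9.1.2). Mental state therefore confounds any association fitted to this variation.

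**Step 3. What the data leave open.** Let f be prompt frequency relative to the study schedule, and let the 12-month cumulative hazard of disengagement be a + b·f. The engagement cost is b. With f = 1 for everyone, the design matrix with columns 1 and f has rank 1 of 2, so only a + b is identified. This model leaves out the confounded variation in Step 2.

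Let D be observed disengagement and s = b/(a + b) the unknown share of the hazard due to prompts. At frequency f:

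D(f) = 1 − (1 − D)^[(1 − s) + s·f]

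Section 6.2.2 cites 85% retention at 12 months in an earlier trial. Taking D = 15% from this as a stand-in for disengagement is an assumption; 30% and 50% are further assumed values.

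- D = 15%, f = 0.5, s = 0: 1 − 0.85 = 15.0%
- D = 15%, f = 0.5, s = 0.5: 1 − 0.85^0.75 = 11.5%
- D = 15%, f = 0.5, s = 1: 1 − 0.85^0.5 = 7.8%

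| Observed D | f | No prompt effect (s = 0) | All due to prompts (s = 1) |
|---|---|---|---|
| 15% | 0.5 | 15.0% | 7.8% |
| 15% | 0.25 | 15.0% | 4.0% |
| 30% | 0.5 | 30.0% | 16.3% |
| 50% | 0.5 | 50.0% | 29.3% |

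Within each row, every value of s reproduces the same observed D at f = 1. Subsampling cannot choose between them.

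**The case against.** The best defence is that the analysis sections are sounder than the summary. Section 6.4.4 already validates on burden and prediction performance, and its promise of unbiased estimates concerns predictive performance. Section 3.5 lists disengagement on its own, and 6.4.3 uses it as an outcome to be predicted, which serves research question 7. Objective 4 speaks of developing a framework for future use, research question 6 asks only which methods show most promise, and the protocol says openly that the algorithm is not deployed. All of this stands, and it keeps the correction small.

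It does not remove the mismatch. The summary and 3.1 still say validate, the summary still names disengagement as the measure, and the future study in 4.1 is about clinical decision-making and does not mention engagement.

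A reader might infer three stronger things that the documents do not support:
- *That the study plans to compare disengagement between regimens.* No analysis section does so.
- *That the engagement cost cannot be estimated at all.* An association could be fitted to the variation in Step 2. The difficulty is that it would be confounded, and reading it as an effect of prompting needs assumptions the data cannot test.
- *That the chosen regimen depends wholly on the assumed cost, and would stay daily at zero cost.* Section 6.4.3 also weighs the value of the observation, and the protocol does not fix a daily schedule: section 5 speaks of prompts through the week, and 5.8.1 only caps completion at once a day.

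The detailed cost values and any tolerated loss in performance may properly sit in the analysis plan; their absence from the protocol is not part of this point.

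**Conclusion.** The point holds for the secondary aim and leaves the primary outcome untouched. The measure named in the summary cannot respond to the regimen, so it cannot validate it. That part follows from the protocol's own statements and needs no numerical assumption. What Group 2 can support is a statement about requests removed against prediction performance lost.

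The cost term in 6.4.3 is not identified without strong untestable assumptions. This rests on the absence of study-set variation in prompt frequency and on the protocol's own description of who disengages. The range of 15.0% to 7.8% for halved prompts shows how wide the uncertainty could be. It depends on the assumed hazard form and on retention from another trial standing in for disengagement, so it is not a prediction for this cohort.

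**What to change.** 1. In the Study Summary and 3.1, restate the aim and its measure to match 6.4.4: derive the regimen, and validate in Group 2 the proportion of requests removed against the loss in relapse-prediction performance.
2. Keep disengagement as a separate descriptive and prediction outcome, as 3.5 and 6.4.3 already do.
3. In 6.4.4, state that engagement benefit is not tested in this study and is left to a later one.
4. In 6.4.3, select the regimen across a stated range of disengagement costs, including zero, and report how the selected regimen changes. The values can be set in the analysis plan, before Group 2 is analysed.

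The cost is a less favourable stated claim and a small sensitivity analysis. No new data and no change for participants are needed.

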#### iv. Funding and Support in kind

Funder(s)	Financial and Non Financial Support Given
The Wellcome Trust	This project is funded by a Wellcome Trust funded grant (222875/Z/21/Z) CONNECT: Digital markers to predict psychosis relapse. The views expressed are those of the author(s) and not necessarily those of the Wellcome Trust.

#### v. Role of Study Sponsor and Funder

Neither the study sponsor nor the study funder will control final decisions regarding study design, conduct, data analysis and interpretation, manuscript writing, and dissemination of results. The proposed project has been reviewed by an international panel of experts convened by The Wellcome Trust and was recommended for funding. The project sponsor is The University of Manchester (UoM) who will oversee study setup, delivery and close-out to ensure research governance compliance. The analysis, interpretation and preparation of outputs will be the responsibility of the Principal Investigator ([name]) and the project team. The views expressed will be those of the authors and not necessarily those of the Wellcome Trust or UoM.

#### vi. Roles and Responsibilities of Study Management Committees / Groups & Individuals

##### **Project Management Group (PMG)**

Operational management and governance of transitions between workstreams will be through monthly meetings of the PMG, chaired by the Principal Investigator (PI; [name]) or her nominated Deputy, and comprising study Co-Investigators (including the site PIs and a Patient & Public Engagement (PPI) co-applicant), the project manager, the recruitment site research co-ordinators and postdoctoral researchers. Meetings will be held primarily remotely. The PMG will monitor study progress, identify risks, and develop solutions to managing risks to ensure the project will be delivered in a timely manner and within budget.

##### **Project Board**

The Board shall comprise of [name], [name], one nominated representative from each academic institution, being Manchester, KCL, Glasgow, Edinburgh, Cardiff, and Sussex and [name] on behalf of McPin (the “Board Members”). All significant operational matters relating to the Project will be decided upon by the Board. The Board shall monitor and assess the progress of recruitment of participants to the study and shall conduct an annual review of each participating site from the date of commencement of recruitment. The Board will meet every 6 months at venues to be agreed and at any time when reasonably considered necessary at the request of any of the Parties.

